5.2.3 General Anesthesia/Sedation

Subject compliance and maintenance of appropriate and stable positioning in the MRI is complicated due to the anticipated behavior disturbances characteristic of MPS IIIB subjects. A key advantage of general anesthesia is that it minimizes any potential for stress or anxiety during the procedure and is independent of a subject's ability to cooperate, which is critical with MPS IIIB subjects. The whole process, including preparation and scan time, is more predictable, and the scan quality will benefit as a result of the subject being immobilized.

Thus, subjects will receive general anesthesia prior to the MRI procedure. In principle all types of general anesthesia techniques can be used as long as the subject is kept asleep during the MRI procedure. The decision should depend on comorbidities, anatomy and fasting status in the individual case and the procedures and practices of the institution. In clinical practice and in earlier studies with subjects with MPS III, propofol sedation was used together with a laryngeal mask to guarantee a secure airway and to not unnecessarily prolong the procedure. The IV properties of propofol make it an ideal anesthetic for subjects undergoing imaging assessments. An IV anesthetic without endotracheal intubation allows for careful titration of sedation to achieve a clinical effect. Propofol provides the ability to titrate an anesthetic level rapidly and maintain stable drug concentrations during the procedure, thus ensuring that anaesthesia is administered in a timely and consistent manner. Recovery from this type of anaesthesia is rapid and not accompanied by nausea or vomiting. Often the anesthetic can be delivered allowing the subject to breathe spontaneously. Competency of airway is accomplished by the insertion of a laryngeal mask airway which allows ventilation of the subject in the cases required. Appropriate local procedures should be utilized under supervision of a pediatric anesthesiologist, however, in subjects aged 2 - 10 years, a dose of 100 mcg/kg/min will be sufficient to keep the subject asleep with no movement during the scan. If the subject has an IV in place, then a bolus of 2-10 mg/kg (depending on age) can be given initially, followed by a continuous infusion of propofol. If no IV is in place, then anesthesia can be induced with an inhalative narcotic such as halothane or sevoflurane (with N20 and oxygen), and IV can be inserted, and then continuous infusion of propofol started (Schulte-Uentrop 2010, Curr Opin Anaesthesiol).

As indicated in Section 5.2.1.4, if clinically appropriate, lumbar punctures may also be performed under general anesthesia in accordance with local institutional procedures. When applicable, the lumbar puncture should be performed just prior to or after the MRI. Lumbar puncture, when not performed alongside the MRI, may also be performed under light sedation.

If clinically indicated, subjects may also receive general anesthesia or sedation for central line placement for long-term vascular access, in accordance with institutional guidelines. When possible, the procedure to place the central line should be performed while the subject is already anesthetized or sedated for another study procedure.

5.2.4 Structural and Diffusion MRI

MRI will be performed at time points specified in the SOA.

High-resolution whole-brain T1-weighted and T2-weighted images will be acquired in order to enable measurements of brain volume and relative volumes of grey and white matter.

Whole-brain diffusion MRI will also be acquired with multiple diffusion sensitization orientations, b value ≥ 1000 s/mm². This will enable measurement of diffusion tensor parameters, including mean diffusivity (mean apparent diffusion coefficient) and fractional anisotropy, as well as anatomical connectivity mapping.

The estimated total scan time will be approximately 5-10 minutes for structural MRI sequences and 15 minutes for diffusion MRI sequences. All imaging scans will be read centrally. Detailed instructions on image acquisition and analysis will be provided in the Imaging Manual.

5.2.5 Telephone Calls

A follow-up telephone call will be made to each subject (or the subject's parent or caregiver) within 24 hours after each of the subject's second, third, and fourth doses (Week 2, Week 4, and Week 6, respectively) in Part A to assess AEs.

If the subject does not participate in Part B or in Part C of the study, an additional follow up telephone call will be made to the subject (or the subject's parent or caregiver) to assess AEs and concomitant medications at least 4 weeks after the subject's last administered dose in either Part A or Part B unless the subject has a scheduled follow-up visit.

If the subject participates in Part C of the study, a follow-up telephone call will be made to the subject (or the subject's parent or caregiver) to assess AEs and concomitant medications at least 4 weeks after the subject's last dose of SBC-103 administered under this protocol unless the subject has a scheduled follow-up visit.

6 STUDY TREATMENTS

6.1 Treatments Administered

Part A (Initial Therapy)

In Part A, all subjects in each dosing cohort (0.3 mg/kg, 1 mg/kg, 3 mg/kg) will receive SBC-103 administered by IV infusion QOW for 24 consecutive weeks. Infusions must be administered at least 10 days apart. All study visits will be scheduled relative to Day 0.

Part B (Therapy at 1 and/or 3 mg/kg)

For eligible subjects, dosing in Part B may not be re-initiated sooner than 4 weeks and no greater than 4 weeks and 3 days after the last dose administered in Part A (See SOA). Subjects who received doses of either 0.3 mg/kg or 1 mg/kg during Part A may escalate to the next higher dose of SBC-103 considered to be safe by the Sponsor and SRC with their first dose in Part B or at any time thereafter. Subjects who received doses of 0.3 mg/kg in Part A may be considered for a second dose escalation to 3 mg/kg at any time during Part B provided that they have tolerated at least 2 doses of 1 mg/kg in Part B (see Section 3.1.2).

In Part B, if a subject misses ≥ 3 consecutive infusions, additional assessments will be required prior to resuming dosing, including safety labs (hematology, chemistry, coagulation, urinalysis and pregnancy test, where applicable), and serum and urine HS. If ≥ 6 consecutive infusions are missed, additional assessments, including lumbar puncture for CSF collection, may be required prior to resuming dosing as determined by the Sponsor in consultation with the investigator. The next scheduled lumbar puncture would not be necessary if ≤ 2 months have elapsed since the previous lumbar puncture.

Part C (Therapy at 5 and/or 10 mg/kg)

Dosing in Part C may start as soon as a subject is eligible (Section 4.3.4) and according to the schema outlined in Section 3.1.3. Therefore, each subject's duration of treatment and assessments in Part B may vary. Once a patient is dose escalated in Part C, the study visit schedule is reset to Day 0 Part C (Day 0C). In Part C, subjects will be randomized such that at least 1 subject from each cohort assigned in Part A will receive SBC-103 at 5 mg/kg and at least 1 subject from each cohort assigned in Part A will receive SBC-103 at 10 mg/kg. Thus each of the assigned dose levels from Part A will be represented in each of the 2 dose levels being studied in Part C. Infusions must be administered at least 10 days apart. All study visits in Part C will be scheduled relative to Day 0C.

6.1.1 Dose Adjustments

The maximum planned dose to be evaluated in this study is 10 mg/kg administered by IV infusion. In the event of poor tolerability at any time during the study the dose may be reduced or paused. If a subject cannot tolerate the lowest dose (0.3 mg/kg QOW) despite measures taken to manage any IARs or other significant safety events, the subject will be discontinued from treatment. See Section 7.1.3 for guidelines for diagnosis and management of IARs and Section 6.2 for stopping rules for individual and multiple patients.

6.2 Stopping Rules

6.2.1 Stopping Rules in Individual Subjects

During Part A (Initial Therapy), Part B (Therapy at 1 and/or 3 mg/kg), and Part C (Therapy at 5 and/or 10 mg/kg), subjects who experience a severe IAR, a serious or severe AE that is

Page 75 of 121

considered related to SBC-103, or a significant elevation in specific laboratory values will have SBC-103 dosing paused based on the rules described below.

For IARs:

- Subjects who develop a severe IAR, as defined in Section 7.1.3, must stop treatment until their information is reviewed by the SRC. Dosing with alterations to the infusion regimen (eg, pretreatment or slowing the rate of infusion) may resume once the SRC and the Sponsor approve.
- Subjects with mild or moderate IARs can continue receiving SBC-103 in the study. The SRC or Sponsor may recommend alterations to the infusion regimen (eg, pretreatment or slowing the rate of infusion).

For all other AEs (ie, AEs that are not characterized as IARs):

- Any event considered related to SBC-103 which is either serious or severe will result in pausing additional dosing in an individual subject. The SRC and the Sponsor will review the data and will resume dosing only after review and agreement.
- Subjects with mild or moderate non-serious AEs can continue receiving SBC-103 in the study.

For Laboratory Values:

- Dosing will be paused based on confirmed elevations in AST or ALT under the following circumstances:
 - In the event that a subject's AST or ALT is greater than or equal to 2 times the ULN (when baseline ALT or AST was within normal limits)
 - In the event that a subject's AST or ALT is greater than or equal to 3 times the ULN (if baseline ALT or AST greater than 1.5 ULN).

Dosing will only resume after AST or ALT have returned to baseline or to study nadir (nadir values may be confirmed by additional lab sampling at the discretion of the investigator, using the same lab for analysis of each sample), or normalized if the baseline level was within normal limits.

The subject should be restarted at a reduced dose. For example, if a subject was receiving a dose of 10 mg/kg, he/she would be restarted at 5 mg/kg; subjects receiving 5 mg/kg would be restarted at 3 mg/kg; etc. In the event that the subject was receiving a dose of 0.3mg/kg, he/she may resume at the 0.3 mg/kg dose only after AST or ALT have returned at least to baseline or to study nadir (nadir values may be confirmed by additional lab sampling at the discretion of the investigator, using the same lab for analysis of each sample), or normalized if the baseline level was within normal limits.

If after resuming treatment at the lower dose, the ALT or AST elevation recurs at greater than or equal to 2 times the ULN (for those with ALT or AST within normal limits at baseline) or 2 times the baseline value (for those with abnormal ALT or AST at baseline) study drug should be stopped and not resumed. Dosing will be paused based on confirmed elevations in AST or ALT with accompanying elevations in the following

• Confirmed bilirubin greater than 1.5 times ULN

- Confirmed INR increase of 0.2
- Eosinophilia (more than 5%), rash or fever

If these bilirubin and INR values normalize (and the independent SRC believes that it is safe to do so), the subject may resume dosing on a lower dose of the study drug (eg, those on a 3 mg/kg would resume dosing at 1 mg/kg, those on a 0.3 mg/kg dose would resume the 0.3 mg/kg dose). However, in this scenario, if a subject develops recurrent elevations in AST or ALT (with or without elevations in total bilirubin or INR), the drug should be stopped and not resumed.

Subjects whose rise in LFTs is accompanied by eosinophilia (more than 5%), rash or fever should not be restarted on the study drug.

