6.2.2 Stopping Rules for Multiple Subjects

At any time during this study, if 2 or more subjects experience the same (or similar) event considered related to SBC-103 which is either serious or severe, or any 1 subject experiences a life-threatening AE considered to be related to SBC-103, **dosing will be paused for all subjects treated at that dose or higher**. The SRC and the Sponsor will review the subject(s) data and dosing will resume only after review and agreement. Detailed information regarding the composition of the SRC, the safety data to be reviewed, and the data review process will be included in the SRC charter.

At any time during this study, the SRC or Sponsor may request a pause in dosing of all subjects based on review of reported events and all available data. Dosing will resume only after the review of data and agreement to do so by the SRC and Sponsor.

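### Section 6.2.1 stops dosing for infusion-associated reactions on severity grade alone, so a first serious but non-severe reaction triggers no mandatory pause for that child

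*Protocol*

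**What the plan says.** The lead-in to Protocol Section 6.2.1 names three grounds for pausing an individual. The first two are in "subjects who experience a severe IAR, a serious or severe AE that is" considered related to SBC-103. The third is a "significant elevation in specific laboratory values will have SBC-103 dosing paused based on the rules described below".

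Three sets of rules follow.

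- **IARs.** A severe IAR stops treatment until the SRC has reviewed it. Subjects with mild or moderate IARs "can continue receiving SBC-103 in the study. The SRC or Sponsor may recommend alterations to the infusion regimen". Seriousness is not mentioned in either bullet.
- **Other adverse events**, introduced by "For all other AEs (ie, AEs that are not characterized as IARs". Here the pause rule is: "Any event considered related to SBC-103 which is either serious or severe will result in pausing additional dosing in an individual subject". The matching rule for continuing is: "Subjects with mild or moderate non-serious AEs can continue receiving SBC-103 in the study".
- **Laboratory values**, which do not bear on this point.

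Table 9 in Section 7.1.3 suspends dosing until SRC review in the row for severe reactions. Section 6.2.2 pauses everyone at the same dose or higher after one related life-threatening event, or "if 2 or more subjects experience the same (or similar) event considered related to SBC-103 which is either serious or severe".

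**The concern.** The continuing rule for other adverse events requires that the event be non-serious. The continuing rule for IARs does not. No reason is given for the difference.

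The Protocol rates severity and seriousness separately (Section 7.1.1), and Section 7.2.1 expressly refers to serious as well as non-serious IARs. An IAR can therefore be graded moderate and still be serious, for example because it led to admission.

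IARs are this study's adverse events of special interest (Section 7.1.3). Section 1.5.2 describes them as the main adverse events of approved enzyme replacement therapies, though usually mild. After such a reaction the next infusion is the re-exposure. In a first-in-human study in children, whether that infusion waits for a safety review should be settled by the rule and not by how a site reads it.

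**Working it through.** No arithmetic applies, so the check is to apply each rule to each kind of related, non-life-threatening event.

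**Step 1. Are IARs related adverse events?** Yes. Under Section 7.1.3 an IAR by timing must be judged at least possibly related, and the second route requires a reaction that the investigator considers related to the drug. Section 7.1.1 classes possibly related as related.

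**Step 2. What do the rules require?**

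| Event | Bullets in 6.2.1 | Table 9 |
|---|---|---|
| Severe IAR, serious or not | Stop until SRC review | Suspend until SRC review |
| Mild or moderate IAR, non-serious | May continue | No suspension |
| Mild or moderate IAR, serious | May continue | No suspension found |
| Other event, serious or severe | Pause until SRC and sponsor agree | Not applicable |
| Other event, mild or moderate and non-serious | May continue | Not applicable |

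The third row is the gap. The same seriousness and severity outside the IAR definition falls in the fourth row and pauses.

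**Step 3. Which events land in the third row?** Take the seriousness criteria in Section 7.1.1 in turn.

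- Death and life-threatening events do not fit a mild or moderate grade, and one related life-threatening event already pauses dosing under 6.2.2.
- A congenital anomaly is not an infusion reaction.
- Significant disability, or an important medical event that puts the subject in jeopardy, sits badly with the definition of moderate, which excludes significant or permanent risk of harm.
- Hospital admission or a longer stay remains. Many admissions would be graded severe, because severe covers interruption of daily activities or a significant effect on clinical status. Table 9 also lists wheezing, stridor and a fall in blood pressure approaching 20-30% as severe.

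What is left is mainly a precautionary admission or a prolonged stay. It is not empty. Every Part A subject is an in-patient for at least 24 hours after the first dose (Section 3.1.1). A reaction with urticaria and vomiting treated with intravenous antihistamine, as in the middle part of Table 9, could prolong that stay without a severe grade.

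**Step 4. Does another rule force an individual pause?**

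- Section 6.2.2 counts subjects, so a mandatory pause for an event in the third row needs 2 affected children, against 1 for the same event outside the IAR definition. A repeat in the same child does not count as a second subject.
- Sections 7.2.1 and 7.4.1 require every IAR to reach the sponsor within 24 hours. That is mandatory reporting, not a mandatory pause.
- The synopsis lets the SRC or sponsor request a pause for an individual, and Section 6.1.1 allows a pause for poor tolerability. Both are discretionary.
- Section 7.5 provides ad-hoc SRC review as needed, including for subjects who meet the stopping rules. Under the bullets this child does not meet them.
- Table 9's pre-treatment and its tryptase and antibody sampling for non-severe reactions assume that a next infusion will be given.

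**The case against.** The strongest reply is that there is only one rule. The lead-in's three grounds match the three sets of rules in the same order, and the lead-in defers to those rules. The second ground belongs with the second set, which excludes IARs. Listing a severe IAR separately would be redundant if the second ground already covered IARs. On this view the protocol chose to manage IARs by severity grade.

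Most of this stands. A reader might infer that Section 6.2.1 contradicts itself, because a serious IAR is literally a related serious adverse event and so falls under the lead-in. The documents do not support that as the natural reading: the specific bullets most plausibly govern. The wording still leaves the intention uncertain, since nothing expressly exempts IARs from the second ground. If the bullets govern, the difference in treatment remains and is unexplained. Section 6.2.2 itself uses serious or severe with no exclusion of IARs.

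The reply is also right that few events are affected, and that the sponsor would normally know of the reaction before the next infusion, because the schedules keep infusions at least 10 days apart.

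Two limits on the evidence also stand. Section 6.2.2 says that "the safety data to be reviewed, and the data review process will be included in the SRC charter", and that charter is not among the documents. Table 9 is imperfectly reproduced in the available text: the heading of its middle row is missing. The surviving text shows no suspension there, but that observation rests on a damaged table.

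**Conclusion.** The concern holds as an unexplained difference in treatment with a narrow reach. One related event that is serious but neither severe nor life-threatening pauses a child if it is not an IAR, and does not if it is.

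The size cannot be given as a number of children, because the documents available give no rate of serious IARs. A reader might tabulate severity against seriousness and take the share of differing combinations as a measure of size. That would mislead, because the combinations in question are expected to be rare. A reader might also infer that a child could be re-infused with nobody aware of the reaction. The 24-hour reporting duty and the power to pause an individual rule that out as the expected course. What is missing is an automatic pause and review.

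The conclusion assumes that the bullets govern over the lead-in, that the SRC charter does not already require the pause, and that the missing text of Table 9 contains no suspension for non-severe reactions. If the lead-in governs instead, the pause already exists and the same edit only makes the wording clear.

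The sponsor stopped development on 11 July 2017 (SAP Section 4), so the point matters mainly for the rule as designed or as reused elsewhere. It is a cheap improvement. No analysis or sample-size figure is affected.

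**What to change.** Bring IARs under the standard that the Protocol already uses for other related events.

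1. In the lead-in to 6.2.1, make the first ground a severe or serious IAR.
2. In the first IAR bullet, require treatment to stop until SRC review for a severe or serious IAR.
3. In the second IAR bullet, limit continuation to mild or moderate non-serious IARs.
4. In Table 9, state that suspension until SRC review applies to any serious IAR, whatever its grade.

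This is three short phrases and one line, with no new data to collect. It needs a documented protocol amendment with investigator signature and, where applicable, ethics approval (Section 11). The clinical cost is an occasional short pause for a serious but manageable reaction. A review finished before the next scheduled infusion costs no dose; a longer one delays or omits an infusion.

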5.2 Clinical Laboratory Assessments

5.2.1 Routine Assessments and Biomarkers

A list of all clinical laboratory tests that will be performed is provided in Table 4; the time points for sample collection are specified in the SOA. Central lab reference ranges will be used throughout the study, including in the event that labs are analyzed locally. All attempts should be made to draw lab samples for central lab analysis when samples are needed for local analysis.

Blood will be collected for standard hematology and serum chemistry (including coagulation parameters).

During Screening, if a subject's ALT or AST is greater than $3 \times ULN$; or a subject has elevated bilirubin or PT/INR, confirmatory testing will be completed. Confirmatory testing may be completed locally or by the central lab, however results will be based on the standardized reference ranges provided in the central laboratory manual for this study. Abnormal safety labs at Screening can be repeated within 1 to 2 weeks. The difference between these two pre-treatment values for each abnormal lab should differ by <20% in each subject.

Efforts should be made by the Investigator to review subject medical history, concomitant medications and health status so that a clear explanation for the elevation is established. The Investigator, in consultation with the Sponsor, shall make a determination of subject eligibility based on review of Exclusion Criteria #8.

During the study, after treatment with SBC-103, in the event that a subject's ALT or AST are $2 \times$ ULN (when baseline ALT or AST were within normal limits) or $3 \times$ ULN (when baseline ALT or AST was greater than $1.5 \times$ ULN), or when a subject has an elevation in bilirubin or PT/INR a confirmatory test should be completed at the earliest possible time point, but not later than the next scheduled visit. Upon positive confirmation of the elevated transaminases as described above, dosing will be paused until AST and ALT have returned to baseline or to study nadir (nadir values may be confirmed by additional lab sampling at the discretion of the investigator, using the same lab for analysis of each sample), or normalized if the baseline level was within normal limits. See Section 6.2.1 for stopping rules.

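### Protocol Sections 5.2.1 and 6.2.1 set no isolated ALT/AST confirmatory-test or pause threshold for a baseline above ULN and up to 1.5 x ULN

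*Protocol*

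**What the plan says.** Protocol Section 6.2.1 has two isolated-enzyme triggers. Dosing pauses if AST or ALT "is greater than or equal to 2 times the ULN (when baseline ALT or AST was within normal limits"), or if it "is greater than or equal to 3 times the ULN (if baseline ALT or AST greater than 1.5 ULN").

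Section 5.2.1 uses the same two bands, the lower one applying "when baseline ALT or AST were within normal limits", to decide when "a confirmatory test should be completed at the earliest possible time point, but not later than the next scheduled visit". A bilirubin or PT/INR elevation triggers that test separately. The pause in Section 5.2.1 then depends on confirmation of a rise in one of the two enzyme bands.

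Three further parts of Section 6.2.1 bear on the point:

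- After a pause, "The subject should be restarted at a reduced dose".
- If the rise recurs after restart, drug stops permanently at 2 x ULN for a normal baseline, or at "2 times the baseline value (for those with abnormal ALT or AST at baseline").
- A separate combined rule has no baseline band: "Dosing will be paused based on confirmed elevations in AST or ALT with accompanying elevations in the following", followed by bilirubin, INR, and eosinophilia, rash or fever.

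On eligibility, exclusion criterion 8 (Section 4.3.2) gives an enzyme example that starts above 3 x ULN and depends on investigator opinion in consultation with the sponsor. Sections 4.3.3 and 4.3.4 reapply the same exclusions for Parts B and C. The SAP adds no stopping threshold; it only lists laboratory data (Section 7.3.3.1).

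**The concern.** A stopping rule divided by baseline should cover every baseline that eligibility admits. This one skips the interval from just above ULN to 1.5 x ULN. Read literally, it keeps dosing a child in that interval through an isolated rise that would pause a child with a lower or a higher baseline, and no reason is given for the difference.

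This is a first-in-human paediatric study. Section 1.3 reports minimal to mild liver inflammation in rats at all tested doses (1, 3 and 10 mg/kg), and Part C gives 5 and 10 mg/kg. Section 1.5.2 names liver monitoring among the risk controls and refers the reader to Sections 5.2 and 6.2 for laboratory assessments and stopping rules. A site that meets the gap must decide case by case, where the protocol otherwise meant the number to decide.

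**Working it through.** The check is whether the rule covers every admissible baseline. Let b be the baseline enzyme value in multiples of ULN. Within normal limits is taken as b ≤ 1.

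**Inputs**

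- First pause: 2 x ULN if b ≤ 1; 3 x ULN if b > 1.5 (Sections 5.2.1 and 6.2.1).
- Permanent stop on recurrence after a pause and restart: 2 x ULN if b ≤ 1; 2b x ULN if b > 1 (Section 6.2.1).
- Eligibility: no enzyme-based exclusion example at or below b = 3 (Section 4.3.2).

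**Coverage**, with both enzymes at the same baseline:

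| b (x ULN) | First isolated pause (x ULN) | Pause ÷ baseline | Recurrence stop (x ULN) |
|---|---|---|---|
| 0.5 | 2 | 4.0 | 2 |
| 1.0 | 2 | 2.0 | 2 |
| 1.01 | none | – | 2.02 |
| 1.2 | none | – | 2.4 |
| 1.3 | none | – | 2.6 |
| 1.5 | none | – | 3.0 |
| 1.51 | 3 | 1.99 | 3.02 |
| 2.0 | 3 | 1.5 | 4.0 |

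The uncovered interval is 1 < b ≤ 1.5.

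**Example.** With both baselines at 1.3 x ULN, a confirmed isolated ALT of 4 x ULN is 4 / 1.3 = 3.08 times baseline. It triggers neither the enzyme-based confirmatory test nor the isolated pause. The same ALT would exceed the 2 x ULN trigger at b = 1.0 and the 3 x ULN trigger at b = 2.0.

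**How the baseline condition is read.** Both sections refer to baseline ALT or AST.

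- Both enzymes in the band: no reading supplies a threshold.
- One enzyme in the band, the other normal: read disjunctively, the normal enzyme brings the child under 2 x ULN; read enzyme by enzyme, the one in the band has no threshold.
- One enzyme in the band, the other above 1.5 x ULN: disjunctively, 3 x ULN applies; enzyme by enzyme, the one in the band again has none.

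**Candidate threshold.** Setting the pause at 2b inside the gap gives 2 x 1.1 = 2.2, 2 x 1.3 = 2.6 and 2 x 1.5 = 3.0 x ULN. At b = 1.0 it equals the existing 2 x ULN, and at b = 1.5 it equals the 3 x ULN that applies just above. It therefore joins the two bands without a step.

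**The case against.** The strongest reply is that the child is not unprotected, and this largely stands. The Synopsis (Methodology) lets the SRC or the sponsor pause an individual child at any time. Section 6.1.1 adds: "In the event of poor tolerability at any time during the study the dose may be reduced or paused". Section 6.2.1 pauses for a related serious or severe AE, and its combined rule works at any baseline. Section 7.2.4 calls for immediate repeat of unexplained, clinically significant values and for hepatologist review of possible drug-induced liver injury. Section 7.5 provides ad-hoc SRC review. An ALT at three times baseline would plausibly be judged clinically significant.

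A reader might therefore infer from the gap that no finding could trigger a first pause. The documents do not support that: the combined rule can. What is missing is narrower, a mandatory trigger for an isolated rise. The routes listed need additional findings or rest on judgement. Section 7.1.2 leaves an out-of-range value off the AE record unless the investigator finds it clinically significant, and Section 7.1.1 grades severity by daily activities, clinical status and treatment need, not by enzyme multiple. An asymptomatic rise could thus be graded mild or moderate, and Section 6.2.1 allows dosing to continue after a non-serious AE of that grade.

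A reader might also infer that every child with one enzyme in the band lacks a threshold. The disjunctive wording does not support that where the other enzyme was normal or above 1.5 x ULN.

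Nor does the recurrence rule show that a child with b = 1.3 would be stopped permanently at 2.6 x ULN without ever being paused. It applies only after a pause and restart, and the clause for recurrence after a combined-rule pause gives no 2 x baseline figure. The recurrence rule shows only that the protocol already contains a threshold for any abnormal baseline.

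Finally, 2 x baseline is a choice, not something the protocol implies. Above 1.5 x ULN its own first-pause and recurrence thresholds differ: at b = 2.5 they are 3.0 and 5.0 x ULN.

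**Conclusion.** The point holds and should be fixed. For 1 < b ≤ 1.5 x ULN, the protocol states neither an isolated-enzyme confirmatory test nor an isolated-enzyme pause. This is certain when both enzymes lie in the interval and conditional on an enzyme-by-enzyme reading otherwise. It assumes only that normal means at or below ULN; it does not depend on which visit supplies the baseline.

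The practical size cannot be estimated. The documents do not say how many of the 11 enrolled children had a baseline in the interval, and they show no affected child. A reader might infer that a child was dosed through a rise that should have caused a pause, but nothing in the documents supports that. The SAP (Section 4) records that the sponsor stopped the development programme on 11 July 2017, so a change may no longer alter dosing in this study. It still matters for reading the laboratory listings and for any reuse of the rule.

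**What to change.** In both Section 5.2.1 and Section 6.2.1, add a third band: for an enzyme whose own baseline is above ULN and up to 1.5 x ULN, require the confirmatory test and pause at 2 x baseline, with the SRC to confirm the choice. This matches the abnormal-baseline recurrence threshold already in Section 6.2.1.

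State also that where another threshold already applies because of the other enzyme's baseline, the lower one governs. Without that sentence the change could loosen the rule. With ALT at 1.3 x ULN and a normal AST, the disjunctive reading now pauses at 2 x ULN, whereas 2 x 1.3 = 2.6. Where the other enzyme is above 1.5 x ULN, the new threshold never exceeds the existing 3 x ULN.

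The drafting cost is a few words in an amendment or clarification letter. The operational cost is possibly a few more pauses, each normally followed by restart at a lower dose (10 to 5, or 5 to 3 mg/kg). In Part C groups of 5 and 6, one such child is 1/5 = 20% or 1/6 = 16.7% of a group. A first pause also exposes the child to permanent discontinuation if the rise recurs at the same 2 x baseline, a real cost in a disease without effective treatment.

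With the programme stopped, the sponsor can check the planned laboratory listings for baselines in this interval and correct the rule before it is used again.
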